# 1. PROTOCOL SUMMARY

# 1.1. Synopsis

A Phase 1, open-label study of intravenous GSK3745417 to evaluate safety, tolerability, pharmacokinetics, pharmacodynamics and determine RP2D and schedule in participants with relapsed or refractory myeloid malignancies including acute myeloid leukemia (AML) and high-risk myelodysplastic syndrome (HR-MDS).

# **Rationale:**

GSK3745417 is an intravenously delivered STING (STimulator of Interferon Genes) agonist currently under evaluation in solid tumors in the FTIH 208850 dose escalation study. Recent evidence has shown that in addition to immune-mediated activity, GSK3745417 exhibits a cytolytic effect, a second mechanism of action, in AML cells in nonclinical studies. STING is expressed at a higher level on AML cells compared with other tumor types [The Cancer Genome Atlas (TCGA) - National Cancer Institute]. The high level of STING expression combined with preclinical evidence of antitumor activity makes AML a suitable indication to establish proof of mechanism and evaluate the clinical activity of GSK3745417. The goal of the study is to identify an RP2D and schedule with a manageable safety profile. Study 209809 is proposed to evaluate safety, pharmacokinetics, pharmacodynamics, and preliminary clinical activity of GSK3745417 in relapsed or refractory AML and high-risk myelodysplastic syndrome (HR-MDS).

Dose Escalation (Part 1)									
	Objectives	Endpoints							
Primary	• To determine the safety, tolerability, and RP2D of a daily dosing schedule (induction) of GSK3745417.	
 
Frequency and severity of Adverse Events (AEs), Serious Adverse Events, (SAEs), Dose Limiting Toxicity (DLT), withdrawals due to AEs
 
							
Secondary	
 
To characterize the pharmacokinetics (PK) of GSK3745417, and relevant metabolites, as applicable, after single and repeat-dose administration.
 
	
 
GSK3745417 concentrations in plasma or PK parameters
 
							
Exploratory									

# **Objectives and Endpoints**

Dose Escalation (Part 1)						
	Objectives	Endpoints				
		 				

г

Dose Expansion (Part 2)								
	Objectives	Endpoints						
Primary	
 
To evaluate clinical efficacy following the daily dosing "induction" period of GSK3745417 in participants with relapsed/refractory AML and HR-MDS.
 
To determine the safety, tolerability, and recommended Phase 2 dose (RP2D) for "maintenance"
 
	
 
Objective response rate (ORR) after the daily dosing "induction" period of GSK3745417
 
Frequency and severity of Adverse Events (AEs), Serious Adverse Events, (SAEs), Dose Limiting Toxicity (DLT), withdrawals due to AEs during "maintenance" dosing
 
						
Secondary	
 
To further evaluate the safety, tolerability of one or more RP2D for maintenance
 
	
 
The following may be included based on the availability of data and appropriateness:
 
AEs, SAE, AESIs leading to dose modifications or delays
 
						
	• To characterize the pharmacokinetics (PK) of GSK3745417, and relevant metabolites, as applicable, after single and repeat-dose administration.	
 
GSK3745417 concentrations in plasma or PK parameters
 
						
Exploratory								

Dose Expansion (Part 2)						
	Objectives	Endpoints				
	CCI					

# **Overall Design and Brief Summary:**

This is a Phase 1, open label, dose escalation study to evaluate safety, pharmacokinetics, and pharmacodynamics of intravenous GSK3745417 in participants with relapsed or refractory AML or high risk MDS.

The study will be conducted in a staged approach consisting of 2 parts. Part 1 will evaluate a dosing schedule of a 5 days on/2 days off schedule for 2 weeks, and then have an additional 2 weeks off dose for observation for a total of 28 days in each cycle (5/2)/5q28d). Once a maximum tolerated dose (MTD) has been established, additional cohorts may be opened to refine dosing frequency optimization. Each cohort will include at least 3 participants and dosing of participants entering the study will be staggered by at least 5 days from D1 of previous patient for the first cohort only. Part 1 will include intra-patient dose escalation for 3 cycles, according to safety and tolerability parameters. The starting dose for Cycle 1 will be escalated in the next dose-escalation cohort until a cohort level starting dose-based MTD is reached. Individual patients may titrate above the starting dose-based MTD based on tolerability. Dose escalation cohorts will start with Cycle 1 at 12.5 µg GSK3745417. Within a cohort for an individual subject the dose may double for Cycle 2, and double again for Cycle 3 based on individual tolerability. The starting dose of subsequent cohorts will increase by 2-fold from Cycle 1 of the previous cohort. Patients may be dose reduced for subsequent cycles if there is lack of tolerability in the previous cycle (Section 6.4). The DLT period will be 28 days starting at Day 1 of Cycle 1 of each cohort. After 3 induction cycles, if a complete response (CR) or partial

response (PR) (IWG) is observed (See Appendix 9) each patient will continue with maintenance weekly dosing at the Cycle 3 dose level until disease progression or unacceptable toxicity. Participants with progressive disease after 3 induction cycles will be withdrawn from study. Participants with stable disease or PR after 3 cycles might receive additional cycles if the assessment by the investigator determined a benefit and GSK Medical Monitor agrees.

For Part 1, approximately 22 participants will receive dosing in the hospital on a 5 days on/2 days off schedule for 2 weeks, and then have an additional 2 weeks off dose for observation. The participant will be observed for at least 24 hours after the final dose in each cycle. All participants will be hospitalized the day before a new dosing cycle starts to receive tumor lysis syndrome (TLS) prophylaxis in line with institutional guidelines (all participants should receive IV fluids  $\pm$  allopurinol as well as alkalinization of urine with renal consult if this is in line with institutional guidance). TLS prophylaxis will continue alongside daily dosing as clinically indicated. To further reduce the risk of TLS, guidance in Section 6.4.1.2 must be followed to determine when daily dosing should be held.

A 5 / 2 / 5 q28d dosing regimen is being evaluated in Part 1 since it is hypothesized that increased dosing frequency of GSK3745417 will enhance the direct cell killing effect by more constantly engaging target. After 3 cycles, if a CR or PR (IWG) is observed, each patient will continue with maintenance weekly dosing at the Cycle 3 dose level until disease progression or unacceptable toxicity. Participants with PR after 3 induction cycles might receive additional cycles if the assessment by the investigator determined a benefit and GSK Medical Monitor agrees.

For Part 2, efficacy will be evaluated after an induction phase in approximately 50 participants, 25 AML participants and 25 HR-MDS participants. The induction phase consists of a treatment regimen cycles at the dose/doses determined to be safe in Part 1 (RP2D). The number of cycles, number of doses investigated in the induction phase, and/or dosing schedule of 5 / 2 / 5 q28d treatment will be determined and may be modified based on a review of safety and PK data generated from Part 1. After the induction phase, patients will continue to either a weekly (Q1W), every three weeks (Q3W), or less frequent dosing schedule for maintenance treatment, if a CR or PR is observed (See Response Criteria for Participants with AML Appendix 9; See IWG Criteria for Response for Participants with MDS Appendix 8). Participants with stable disease or PR after 3 induction cycles might receive additional cycles if the assessment by the investigator determined a benefit and GSK Medical Monitor agrees. Up to three dose levels for maintenance treatment will be evaluated in the maintenance dose escalation. The DLT period for the maintenance dose escalation portion of Part 2 will be 28 days starting at Day 1 of each cycle. Dose escalation for the maintenance schedule will start at the highest dose cleared for safety in Part 1. Part 2 will evaluate the efficacy of the induction regimen separately for AML and HR-MDS as well as the tolerability and duration of response of the Q1W or Q3W maintenance schedules to determine the best dose and schedule for further studies.

# Number of Participants:

Approximately 22 participants may be enrolled in Part 1, and approximately 50 participants may be enrolled in Part 2. The total number of participants to be enrolled is an estimate and will depend on the number needed to adequately characterize the DLT and PD profile and determine the MTD(s)/RP2D(s). All participants who take at least one dose of study intervention will be considered evaluable for analysis.

# **Intervention Groups and Duration:**

The study includes a screening period, a treatment period (consisting of - 3-cycle induction phase and a maintenance phase), and a follow-up period. Participants will be screened for eligibility beginning up to 4 weeks before the start of treatment. GSK3745417 will be centrally administered IV according to the dosing schedule in the corresponding cohort the participant is enrolled.

Participants will be assessed for response according to the IWG response criteria for AML or MDS at end of each induction cycle including (at 28 days [after Cycle 1], at 56 days [after Cycle 2], and at 84 days [after Cycle 3]). Within the maintenance phase, assessment will be at 3 weeks and then every 6 weeks thereafter. Participants will be treated until disease progression, unacceptable toxicity, withdrawal of consent, or termination of the study by GSK.

# Data Monitoring/ Other Committee: No

# 1.2. Schema

Part 1: Dose Escalation Cohorts for Daily Dosing MTD

# Figure 1 Part 1 Induction Intra-patient Dose-Escalation Study

\* Patients in C3 dose level in all cohorts will be continuing dosing Q1W at C3 dose level

# Figure 2 Part 1: Dosing and Observation Timeline for Each Cycle

# Figure 3 Part 2: Expansion Study: Induction and Maintenance Dose Escalation

# 1.3. Schedule of Activities (SoA)

- The schedule of activities for each Part of the study may be found on the following pages. For all parts, the following apply:
- The timing of planned study assessments may change during the study based on emerging data/in-stream data review to ensure appropriate monitoring.
- Any changes in the timing of time points for any planned study assessments as the result of emerging pharmacokinetic/pharmacodynamic data from this study must be documented and approved by the relevant study team member and then archived in the sponsor and site study files but will not constitute a protocol amendment.

- The Competent Authority (CA) and ethics committee (EC) will be informed of any safety issues that constitute a substantial amendment and require alteration of the safety monitoring scheme or amendment of the informed consent form (ICF). The changes will be approved by the CA and the EC before implementation.
- For Part 1, Table 1 applies to Cycles 1, 2, and 3 in the Dose Escalation Cohort After completing the assessments in Cycle 3, participants would proceed to complete the assessments in Table 3 for the maintenance phase.
- For Part 2, after completing the assessments in Table 2, participants would proceed to complete the assessments in either Table 3 or Table 4 for the maintenance phase.

# 1.3.1. Part 1 – Dose Escalation

# Table 1 Schedule of Activities: Part 1 - Dose Escalation Cohort(s)

DE Cohort	Screening a	Screening a Cycle (Induction Period)		on Period)	Follow-Up (post-final dose administered)		
Study Procedure		Interven (In-F	tion Period Patient)	Observation Period (Outpatient)	TDV⁵	Follow- Up	Notes
Week	≤4	1	- 2	3 - 4	+4		
Day	≤28	-1	1 - 13	14 - 28	+30d		
Informed Consent	Х						
Inclusion and Exclusion criteria	X						
Demographics, Medical History, Prior Medications, Disease Characteristics	x						Include use of antibiotics, probiotics and anti-infectives taken 60 days prior to study intervention.
Anticancer Therapy and Response to Prior Anticancer Therapy	x						
Participant Registration	x						
Safety Assessments		-	-				
In-House Monitoring		х	x				Participants should be monitored in a medically qualified unit/clinic/hospital starting on Day -1 through Day 13 (24 hours after the administration of GSK3745417 on Day 12) of each cycle.
Physical Exam	X		x		х		A complete physical exam is required at screening, including cardiac and neurological examinations; brief or targeted physical exams will be performed on Day 1 at predose (within 1h prior to dosing) and

# CONFIDENTIAL

DE Cohort	Screening a	Су	cle (Inductio	on Period)	Follov (post-fin adminis	w-Up al dose stered)	
Study Procedure		Intervent (In-P	tion Period atient)	Observation Period (Outpatient)	TDV⁵	Follow- Up	Notes
Week	≤4	1	- 2	3 - 4	+4		
Day	≤28	-1	1 - 13	14 - 28	+30d		
							Day 13 of each cycle, and as clinically indicated. Refer to Section 8.2.1 for physical examination details.
ECOG PS	Х		Х		Х		Should be assessed at each cycle
Vital Signs	x	х	Х		Х		Should be collected at each cycle at least 6 times on Day -1 within 24 hours prior to dosing, Day 1, 5, 8, and 12 at predose (within 1h prior to dosing), end of injection (EOI)+30m, +1h, +2h, +4h, +6h, +8h, +12h, +24h and, at least four times every day until discharge or more frequently if clinically indicated.
Weight	Х	Х			Х		Should be collected at each cycle.
Echocardiogram	X	Week 1	and then Q8 may occur	W. Additional echo as clinically indica	ocardiography ted		If available, a 3D ECHO is preferred, otherwise a 2D ECHO may be performed. Where the quality of the ECHO examination is sub-optimal, MUGA scans may be used. The modality used at baseline should be repeated throughout the study to ensure comparison to baseline. At TDV, ECHO/MUGA does not need to be performed if an on-study ECHO has been conducted within the 4 weeks prior to visit. ECHO should be performed in the final week of the observation period.
IV Contrast-enhanced Brain MRI (preferred) or IV Contrast-	x		Repeat i	f clinically indicate	d		Scans performed as standard of care prior to study consent will be acceptable as long as assessment is Brain imaging to be performed only if clinically indicated.

Safety Laboratory Ass	essments						
Human Immunodeficiency Virus (HIV), Hepatitis B Surface Antigen (HBsAg), Hepatitis C Virus (HCV) Antibody	x						

## CONFIDENTIAL

DE Cohort	Screening a	Cycle (Induction Period)			Follow-Up (post-final dose administered)		
Study Procedure		Intervention Period (In-Patient)		Observation Period (Outpatient)	TDV⁵	Follow- Up	Notes
Week	≤4	1	- 2	3 - 4	+4		
Day	≤28	-1	1 - 13	14 - 28	+30d		
Pregnancy Test	х		≤72 hours (serum)	Х	Х	Q12W	Negative serum pregnancy test required at screening and within 72 hours prior to date of first dose of study treatment for females of childbearing potential. Urine pregnancy test will be conducted every 4 weeks for duration of study, on last day of treatment (if possible), at TDV, and at the Follow-Up visit.
CBC with differential	x	х	Х	Х	Х		Sample collection times: Single sample from Day -1 to Day 13, prior to each administration of GSK3745417. At least every 6 hours for the first 48 hours following initiation of daily dosing period, then at least twice daily up to an including Day 5 dosing of each daily dosing period, and more frequently as clinically indicated. On the days when GSK3745417 is not administered, samples will be collected at approximately the same times as on the days of GSK3745417 administration. A sample will also be taken between Day 20 and Day 22 during the outpatient period of the cycle.
Clinical Chemistry (including laboratory parameters for TLS diagnosis and management)	x	х	х	Х	Х		Sample collection times: Cycle 1, and any cycle with a dose increase: single sample on Day –1; Days 1 and 2 at predose, EOI+6h, +12h, +18h and +24h; Days 3 - 5 – at predose and EOI+6hrs; Days 6 and 7 – single daily

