## CONFIDENTIAL

DE Cohort	Screening a	Cycle (Induction Period)			Follov (post-fina adminis	v-Up al dose stered)	
Study Procedure		Intervention Period (In-Patient)		Observation Period (Outpatient)	TDV⁵	Follow- Up	Notes
Week	≤4	1	- 2	3 - 4	+4		
Day	≤28	-1	1 - 13	14 - 28	+30d		
							sample, Days 8 - 12 – at EOI+6hrs: Day 13 – single sample prior to discharge. Clinical chemistry including uric acid and phosphate will be measured at least every 6 hours for the first 48 hours following initiation of daily dosing period, then at least twice daily up to an including Day 5 dosing of each daily dosing period, and more frequently as clinically indicated. Clinical chemistry samples should be collected more frequently if clinically indicated (such as cases of TLS). A sample will also be taken between Day 20 and Day 22 during the outpatient period of the cycle. See Section 10.2 for complete list of required laboratory assessments.
C-Reactive Protein	x		Х	Х	х		Sample collection times: Day 1 at predose, EOI+8h and +24h for first dose, then pre dose at Day 5 and Day 12 of each cycle.
Thyroid function c	X		Х		x		Sample collection times: Day 1 at predose of Cycles 1 and 3.
Troponin I and T	х		Х		Х		See Section 6.4.1.5 for management of cardiac events. Samples will be collected on Day 13.
BNP (or NTproNBNP)	Х	Repeat as clinically indicated					Repeat test as outlined in management of cardiac events (Section 6.4.1.5)
eGFR	Х						See Section 7.1.2 for management of renal events (if needed).

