# CONFIDENTIAL

DE Cohort	Screeningª	Cycle (Induction Period)			Follov (post-fin adminis	w-Up al dose stered)	
Study Procedure		Intervent (In-P	tion Period atient)	Observation Period (Outpatient)	TDV⁵	Follow- Up	Notes
Week	≤4	1	- 2	3 - 4	+4		
Day	≤28	-1	1 - 13	14 - 28	+30d		
Urinalysis⁰	x		Х		Х		Sample collection times: Days 1, 8 and 13 of each cycle. If urinalysis is abnormal, a microscopy should be performed.
Coagulation	x		х				Sample collection times: at screening and prior to administration of first dose of GSK3745417 and at Day 8 of each cycle. Additional coagulation samples should be collected in the event of CRS (see Section 6.4.1.4)
Study Intervention	•						· · ·
Administer GSK3745417			X				GSK3745417 will be administered the same dose within each cycle on Days 1 – 5 and Days 8 - 12 QD. Participants will receive up to 3 cycles of treatment before moving to Q1W or Q3W dosing (Section 6.1). See Section 4.1 for maximum duration of study intervention. See Section 4.1 for safety and tolerability parameters to be reviewed prior to each daily dose
Non-Azole Antifungal		х	Х	Х			Non-azole antifungals should be administered if indicated, per local standard, on Day -1 through Day 28 of each cycle.
Tumor Lysis Syndrome Prophylaxis		x					All participants should receive tumor lysis syndrome (TLS) prophylaxis prior to date of first dose of each cycle on Day -1 according to institutional guidelines (e.g., participants should receive IV fluids ± allopurinol and consider alkalization of urine and

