#### CONFIDENTIAL

209809 Protocol

DE Cohort	Screening a	Су	cle (Inductio	on Period)	Follow-Up (post-final dose administered)		
Study Procedure		Intervention Period (In-Patient)		Observation Period (Outpatient)	TDV⁵	Follow- Up	Notes
Week	≤4	1 - 2		3 - 4	+4		
Day	≤28	-1 1 - 13		14 - 28	+30d		
CCI							

Abbreviations: AE= adverse event; AESI=adverse events of special interest; CBC=Complete blood count; d=day; ECG=electrocardiogram; ECHO=echocardiography; ECOG PS=Eastern Cooperative Oncology Group Performance Score; eGFR= Estimated glomerular filtration rate; EOI=end of injection; h=hour; ICF=informed consent form; m=min; Q1W=Every 1 week; Q3W=Every 3 weeks; Q6W=Every 6 weeks; Q9W=Every 9 weeks; Q12W=Every 12 weeks; SAE=serious adverse event; W=week; TLS = Tumor Lysis Syndrome; TDV=treatment discontinuation visit

Timepoint Definitions for assessments:

X = Anytime during visit (sampling date/time should be recorded) Predose = within 60 minutes before the start of the GSK3745417 injection EOI+5m = at 5 minutes  $\pm 2$  minutes from the end of the GSK3745417 injection EOI+15m = at 15 minutes  $\pm 5$  minutes from the end of the GSK3745417 injection EOI+30m = at 30 minutes  $\pm 5$  minutes from the end of the GSK3745417 injection EOI+45m = at 45 minutes  $\pm 5$  minutes from the end of the GSK3745417 injection EOI+45m = at 45 minutes  $\pm 5$  minutes from the end of the GSK3745417 injection EOI+1h = at 1 hour  $\pm 15$  minutes from the end of the GSK3745417 injection EOI+2h = at 2 hours  $\pm 30$  minutes from the end of the GSK3745417 injection EOI+2h = at 2 hours  $\pm 30$  minutes from the end of the GSK3745417 injection EOI+4h = at 4 hours  $\pm 30$  minutes from the end of the GSK3745417 injection EOI+6h = at 6 hours  $\pm 30$  minutes from the end of the GSK3745417 injection EOI+8h = at 8 hours  $\pm 1$  hours from the end of the GSK3745417 injection EOI+2h = at 12 hours  $\pm 1$  hours from the end of the GSK3745417 injection EOI+12h = at 12 hours  $\pm 1$  hours from the end of the GSK3745417 injection EOI+12h = at 12 hours  $\pm 1$  hours from the end of the GSK3745417 injection EOI+12h = at 12 hours  $\pm 1$  hours from the end of the GSK3745417 injection EOI+12h = at 12 hours  $\pm 1$  hours from the end of the GSK3745417 injection EOI+12h = at 24 hours  $\pm 2$  hours from the end of the GSK3745417 injection

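### In induction Cycles 2 and 3 without a dose increase, Tables 1 and 2 schedule no chemistry sample on Days 6, 7 or 13, so none before discharge

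*Protocol*

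**What the plan says.** The schedule in question is the chemistry row of Table 1 (protocol Section 1.3.1). Table 2 (Section 1.3.2) repeats its wording. Section 1.3 gives the scope: "For Part 1, Table 1 applies to Cycles 1, 2, and 3 in the Dose Escalation Cohort".

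The note in the chemistry row has three timed parts:

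- A day-by-day list that opens "Cycle 1, and any cycle with a dose increase: single sample on Day" -1. It then gives five times on each of Days 1 and 2, two on each of Days 3-5, one sample on each of Days 6 and 7, one at EOI+6h on each of Days 8-12, and one on Day 13 before the participant leaves hospital.
- A general sentence with no cycle limit: six-hourly for the opening 48 hours, "then at least twice daily up to an including Day 5 dosing of each daily dosing period".
- One outpatient sample: "A sample will also be taken between Day 20 and Day 22 during the outpatient period of the cycle".

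It also allows more frequent sampling when clinically indicated. The grid carries an X for Day -1 and for Days 1-13, which the table key defines as any time during the visit.

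The CBC row directly above is written differently. It asks for a "Single sample from Day -1 to Day 13, prior to each administration of GSK3745417", with no condition on cycle or dose, and adds: "On the days when GSK3745417 is not administered, samples will be collected at approximately the same times" as on dosing days.

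Section 6.4.1.2 makes six-hourly chemistry over the first 48 hours mandatory in the first cycle and in cycles with a raised dose. It attaches that condition to nothing else.

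**The concern.** As written, the dose-increase condition governs the whole list through Day 13. In a Cycle 2 or 3 at an unchanged or reduced dose the list falls away, and the general sentence is the only timed inpatient requirement left. That sentence stops at a Day 5 dose, so the two rest days between the dosing blocks and the day of discharge have no scheduled chemistry.

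Several rules need a chemistry result before they can act: the creatinine hold in Table 13, the TLS and electrolyte hold in Section 6.4.1, and the liver stopping criteria in Section 7.1.1 and Appendix 7. Table 5 relies on the schedule of activities for frequent chemistry as its TLS and renal monitoring. A creatinine, electrolyte or ALT change can be silent, and a test ordered only when clinically indicated needs a prior suspicion.

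The affected cycles are not only the uneventful ones. They include cycles where escalation was barred under Section 6.4.1.1 by a Grade 3 or higher event or by repeated Grade 2 CRS, and cycles given at a reduced dose under Section 4.1. Participants who tolerated the drug least well can therefore be on the thinner written schedule.

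**Working it through.** No sample-size or error-rate formula applies. The check is a day-by-day count of Days 1-13 against the chemistry row.

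**Inputs.** Dosing days are 1-5 and 8-12 (Table 1, administration row). Inpatient Days 1-13 are from Table 6. Sampling times are from the chemistry row of Table 1. *Daily dosing period* is not defined, so both readings are run.

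**Reproducing the plan's figure.** Doses per cycle = 5 + 5 = 10, which matches the 10 doses stated in Section 4.1.2.

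**Cycle 1 or a dose-increase cycle.** Listed samples on Days 6-13 = 1 + 1 + 5 + 1 = 8. Of these, Days 6, 7 and 13 account for 3. No day from 1 to 13 is uncovered.

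**Cycle 2 or 3 without an increase.**

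| Reading of the period | Days covered by the general sentence | Days 1-13 with no timed sample | Doses on days with no timed sample |
|---|---|---|---|
| Each five-day block | 1-5 and 8-12 (10 days) | 13 - 10 = 3: Days 6, 7, 13 | 0 of 10 |
| The two-week period | 1-5 (5 days) | 13 - 5 = 8: Days 6-13 | 5 of 10 (Days 8-12) |

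Days 6, 7 and 13 are uncovered on both readings.

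**Interval from the last timed inpatient sample to the Day 20-22 sample.**

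- Cycle 1, from Day 13: 20 - 13 = 7 to 22 - 13 = 9 days.
- Block reading, from Day 12: 20 - 12 = 8 to 22 - 12 = 10 days.
- Two-week reading, from Day 5: 20 - 5 = 15 to 22 - 5 = 17 days.

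**Which reading.** The word *each*, and a 5-on, 2-off, 5-on schedule in which Day 5 ends a block, support the block reading. Two things point the other way. Table 5 uses the phrase for the two-week span. The block reading would also put six-hourly and then twice-daily sampling on Days 8-12, where the explicit Cycle 1 list asks for one sample a day. The documents do not settle it.

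**Number of affected cycles.** This is not given. Escalation is permitted, not required, for Cycles 2 and 3, so the range is 0 to 2 per participant.

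**The case against.** The strongest reply is that chemistry is far from absent in these cycles:

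- Section 6.4.1.2 asks for TLS risk, including renal function, to be assessed before every dose. Table 1 adds: "See Section 4.1 for safety and tolerability parameters to be reviewed prior to each daily dose".
- Section 6.4.1.4 requires daily chemistry with liver tests for the first week whenever CRS is suspected, in any cycle.
- Section 6.4.1 adds liver and chemistry tests during a CRS hold, as clinically indicated.
- Table 13 requires creatinine at least every 24 hours once it has risen.
- The grid X for Day -1 precedes the next cycle's first dose, and the Day 20-22 sample comes before that.
- Days 6, 7 and 13 carry no dose, so no dose is given on them without a check. Participants are monitored inpatients throughout.

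Most of this stands, and it limits the point. In particular, a reader might infer that participants with earlier CRS go unmonitored. The documents do not support that, because suspected recurrence itself triggers daily chemistry.

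A reader might also infer that half the doses, with a 15-17 day interval, have no timed chemistry. That needs the two-week reading, which the word *each* counts against. On the block reading, Days 8-12 are sampled and the interval to the outpatient sample is one day longer than in Cycle 1. Even on the two-week reading, renal function is to be assessed before each of those doses.

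The reply does not close the gap on Days 6, 7 and 13. The pre-dose checks attach to doses, the CRS and creatinine rules need an event to start them, and the X fixes no day.

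It can also be said that lighter sampling outside Cycle 1 and dose-increase cycles is deliberate. Section 6.4.1.2 supports that for the six-hourly sampling only. The CBC row shows that the rest days and Day 13 were meant to be sampled for blood counts in every cycle.

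**Conclusion.** The point holds as a minor gap in the written schedule. In induction Cycles 2 and 3 without a dose increase, 0 chemistry samples are scheduled on Days 6, 7 and 13, against 3 in Cycle 1, and none is scheduled before discharge. This does not depend on how the dosing period is read. A site following the tables literally could discharge a participant on Day 13 with no chemistry scheduled since the second dosing block (block reading) or since Day 5 (two-week reading). What is lost is scheduled detection of silent creatinine, electrolyte or ALT changes between the blocks and at discharge.

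The conclusion assumes that the opening condition governs the whole list through Day 13, as the text reads. Section 6.4.1.2 and the CBC row suggest that this was not intended, which makes it a drafting error more than a chosen reduction. Nothing in the documents shows that harm occurred or how many cycles were affected. Under SAP Section 4.8 Part 2 recruited no one, so the Table 2 half concerns the written plan only. Part 1 had finished recruitment at termination.

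**What to change.** In the chemistry cells of Tables 1 and 2:

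1. Limit the Cycle 1 and dose-increase condition to the intensive Day 1-2 times.
2. State that every induction cycle has a single chemistry sample on Days 6, 7 and 13, taken with the CBC draw and, on Day 13, before discharge. Require at least one sample on each of Days 8-12, at EOI+6h.
3. State that the Day 5 rule refers to Days 1-5 of the cycle.
4. Leave Day 1-5 sampling otherwise unchanged. The general sentence already asks for at least two samples a day after the first 48 hours.

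If the sponsor meant the block reading, item 3 would lower the written minimum on Days 8-12 to that of the Cycle 1 list. In that case the sponsor should keep the denser rule for those days and add only Days 6, 7 and 13.

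The cost is wording in two tables plus 3 tubes per affected cycle, or up to 8 on the two-week reading. Over at most two affected cycles that is 2 x 3 = 6, or 2 x 8 = 16, per participant. Participants are already inpatients to Day 13, and blood is already drawn on Days 6, 7 and 13 for CBC. Cycle 1 carries the same list under the 275 mL per four-week limit in Section 8. The documents do not give the volume of a chemistry tube.
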